Appendix C (The IRB-approved Protocol)

SHEDS-Multimedia); however, few model evaluations have been conducted for other chemical types. These models need to be evaluated for consumer product active ingredients because of their prevalence in the indoor environment and potential asthma morbidity in young children from potential exposures. Biomarker measurements will be collected in order to evaluate objective 6. Results from objective 2 will be employed to assist in these analyses.

To accomplish objective 7 we will evaluate a novel method for rapidly characterizing consumer product inventories in the residential environment. We hypothesize that pictures can be used to adequately capture information on consumer products being used in the home. The results from this effort will then be used to predict exposures to chemicals.

There is a lack of current information on children's activities, locations, and dietary habits, and objective 8 will generate such information. We hypothesize that children's activities, locations, and dietary habits are dependent on age, lifestage, and factors related to their home and community. In combination with multimedia measurements being collected in the Green Housing Study, results from this objective will be used to estimate aggregate and cumulative exposures.

Results from objective 9 will be used for the DNA analysis of mold from dust and measurements of the ERMI values at each time point. We hypothesize that the electrostatic dust collection method is adequate to collect enough dust for DNA analysis. From these electrostatically collected molds, DNA will be extracted and analyzed using HTS analysis. HTS technologies provide the opportunity to holistically explore and identify diverse indoor fungal populations. In addition, the metagenomic data generated from the DNA of dust samples will be used to identify genes and functions that are overrepresented among the fungal biota.

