Appendix C (The IRB-approved Protocol)

inventory) to assess collection accuracy. The barcode-based inventory will serve as the standard against which the image-based inventory will be evaluated. For quality control purposes, collection of the consumer product use frequency information may be administered more than once.

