Appendix C (The IRB-approved Protocol)

Objective	Measurements Required	Proposed Analysis Approach

5) Examine the relationships between consumer products in a residence, environmental concentrations, and exposure to active ingredients found in consumer product chemicals to support development and evaluation of models for predicting exposure to these chemicals
	
Household consumer product inventories, house dust, surface wipes, air, blood, urine concentrations
	
Quantification of relationships among media (dust, wipes, air) concentrations by chemical (correlations within and between subjects, descriptive statistics of ratio of air concentrations to surface concentrations); correlation between media (air and dust) concentrations and biomarker concentrations (within and between subjects by chemical); comparison of chemicals (individual or by class) in products found in the home with those found in dust and air (presence/absence) based on available databases of chemical ingredients; comparison of chemicals (individual or by class) in product categories reported as used in the home with those found in media (presence/absence, correlation of magnitude with reported use frequencies) based on available databases of chemical ingredients

6) Measure biomarkers of consumer product chemicals for young children in conjunction with environmental measurements to evaluate exposure and dose models
	
House dust, air, duplicate diet, blood, urine concentrations; activity information; survey information
	
Descriptive statistics; correlation analyses; uni- and multi-variate analyses for biomarker measurements; model runs (e.g., SHEDS, PBPK model, PROCEED) for forward/reverse dosimetry; comparison (t-test, correlations) between measurements and model predictions

7) Assess rapid, low burden, low cost methods for characterizing consumer product use in the residential environment to predict exposure to chemicals
	
Photographs of storage locations for household cleaning products and personal care products; barcode scanner inventory of products
	
EPA investigators will identify products in the photographs (blinded to scanner inventory). Image-based inventories will be evaluated against barcode-based inventories to assess collection accuracy (number of products correctly identified in photo divided by number in scanned inventory)

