Appendix C (The IRB-approved Protocol)

Objective	Measurements Required	Proposed Analysis Approach
8) Use low burden techniques and survey instruments to collect current information on children’s activities, locations, and dietary habits to support exposure models and databases	Survey responses from questionnaire; GPS; accelerometer data	Descriptive statistics of reported time spent in microenvironments and activities; calculation of GPS-based time spent in microenvironments using MicroTrac model; quantitative comparison of questionnaire location results with GPS location results (paired t-test, correlations); quantification of accelerometer-based energy expenditures using accepted modeling methods; descriptive statistics of predicted energy expenditures by microenvironment and activity; coding of activity and location data in time-series format appropriate for exposure modeling
9) Use settled dust to identify and classify indoor fungal populations and functions overrepresented among fungal biota	Fungal DNA extracted from dust samples	Qualitative analyses: HTS; identification and classification of indoor fungal population(s); identification of genes and functions overrepresented among the fungal biota Quantitative analyses: ERMI; correlations; univariate and multivariate analyses; comparisons between pre- and post-renovation time points; renovated and non-renovated homes; comparison of collected dust types
10) Evaluate the feasibility of using a simplified mass balance approach to estimate chemical exposure and dose rates incorporating children’s toenail clippings, other multimedia measurements, and activity information	House dust, soil, hand wipe, surface wipe, duplicate diet, urine, blood, feces, toenail clipping concentrations	Descriptive statistics; univariate and multivariate analyses to compare chemical concentrations; correlations amongst chemicals and media; linear regression modeling incorporating multimedia measurements and survey information; geometric mean and standard deviation for elements measured in multimedia samples by pre- and post-renovation time points

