Survey data include questionnaire responses, activity data, housing data, and product data. An important part of the pilot study is to assess the completeness and quality of survey data. To address the objectives in this research protocol, several approaches (e.g., barcode scanning, product photograph inventory, GPS, accelerometer) are being employed to collect personal, housing, and community exposure factor information for children. Results from traditional survey methods will be compared to collected data. For the questionnaire results, data quality analyses will be completed (as described in objective 8). There are several factors that will be examined to assess quality and suitability for use of the survey variables in exposure assessment. One goal is a $>90\%$ completeness rate for each survey variable. Comprehension and ability to provide requested information will be assessed through discussions with the field study team. Survey data will be examined to ensure that there exists a sufficiently diverse response range to be useful in distinguishing characteristics and activities where relevant in data analysis. The activity and location data collected using the questionnaire will be compared with the GPS and accelerometer data. Consumer product photographic inventory results will be compared to barcode scanning results for the products.

Following the initial step of assessing the measurement data quality and suitability for exposure assessment, EPA proposes to work collaboratively with CDC in exploring how the use of selected pilot study metrics may enhance the understanding of relationships between environmental exposures, activity, and asthma in the main Green Housing Study. The pilot study metrics, including the additional environmental measures and activity information, could be additional explanatory variables for asthma or could modify relationships for variables already collected in the main Green Housing Study. A goal of this evaluation is to identify which metrics may be candidates for incorporation into the full protocol at future Green Housing

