Appendix C (The IRB-approved Protocol)

If samples sizes allow, the study participant data may be stratified (e.g., low/high concentrations, activity, age) to determine if the model can also predict differences between groups. If comparison of model predictions and measurements reveal large discrepancies, the Probabilistic Reverse dosimetry Estimating Exposure Distribution (PROCEED) tool can be used to reveal exposure, data, or model gaps that require additional consideration. As resources, time, and data suitability allow, we will explore relationships for biomarker measurements between blood and urine and compare biomarkers indicating stress (cortisol, cytokines) with multimedia measurements, health status, and exposure factors (personal, housing, community). These relationships will be investigated using methods such as analysis of variance (ANOVA) and principal component analysis (PCA).

Objective 7: Assess rapid, low burden, low cost methods for characterizing consumer product use in the residential environment to predict exposure to chemicals

The information collected in the consumer products inventory and use frequency sections of the questionnaire will be analyzed to address research questions related to children's exposures to chemicals. EPA staff will work in teams to identify the products in the inventory pictures. The product types will then be entered into an electronic database for further electronic processing and analysis. Data analysis will consist of (1) comparison of photo-based inventory to barcode-based inventory and (2) evaluation of consistency between repeated product usage frequency surveys. Additionally, the chemical ingredients can be used to inform the laboratory analyses of the multimedia measurements (objective 5).

Objective 8: Use low burden techniques and survey instruments to collect current information on children's activities, locations, and dietary habits to support exposure models and databases

The information collected in the EPA pilot study add-on questionnaire will be analyzed to develop mean and variability metrics of exposure factors for the children's cohorts being studied, and to identify interactions or correlations among exposure factors that could be used to derive relationships for future assessments of children.

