Appendix C (The IRB-approved Protocol)

B. Location Questions (To be completed by field technician and participant)

3. For each approximate time period given below, indicate where your child was located. Select any locations that apply to the time period.

	Home	Outdoor area at home	Other residence (ex. babysitter's house)	Store	Restaurant	Church	Other indoor location	Park	Bus/train stop	On or near street	Parking garage	Other outdoor location	In vehicle	Don't know/Refused to answer
5:00 am - 5:29 am														
5:30 am - 5:59 am														
6:00 am - 6:29 am														
6:30 am - 6:59 am														
7:00 am - 7:29 am														

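### The statistics named for the photo inventory and for questionnaire versus GPS cover sensitivity, association and mean bias, but not false listings or agreement for the individual child

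*Protocol*

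**What the plan says.** **Photo inventory.** Section 4.6 has the technician photograph the product storage places and also scan the products. It adds: "The barcode-based inventory will serve as the standard against which the image-based inventory will be evaluated". Table 8, Objective 7, has the photo readers work without sight of the scan ("EPA investigators will identify products in the photographs (blinded to scanner inventory") and gives one accuracy measure, the "number of products correctly identified in photo divided by number in scanned inventory". The Objective 7 text in Section 5.0 adds only "comparison of photo-based inventory to barcode-based inventory and (2) evaluation of consistency between repeated product usage frequency surveys". The hypothesis in Section 2.2 is: "We hypothesize that pictures can be used to adequately capture information on consumer products being used in the home". No figure is attached to it.

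**Questionnaire versus GPS.** Table 8, Objective 8, names a "quantitative comparison of questionnaire location results with GPS location results (paired t-test, correlations"). For Objective 2, Table 8 names correlations between survey and device data, and the Section 5.0 text says: "The activity and location data collected using the questionnaire will be compared with the GPS and accelerometer data". The Objective 8 text refers to the method of a cited GPS model-evaluation study without naming an index. Item 3 of the questionnaire (the protocol's own Appendix C) uses half-hour rows with the instruction "Select any locations that apply to the time period".

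**Use of the results.** Objective 4 takes chemical ingredients from the inventory obtained under Objective 7 and models residential concentrations from them. Under Objective 8, time-activity data of adequate quality would go into EPA's public activity database as minute-by-minute diaries. Objective 2 is to identify which metrics are candidates for later sites.

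**The concern.** These comparisons are meant to show whether a cheaper method can stand in for another one. That needs two things the named statistics do not supply.

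For the photos, a reader of the results needs to know how many listed products were really there, as well as how many scanned products were found. Wherever the photo list serves as the inventory, an item that is not in the home brings its ingredients into the exposure prediction, and the stated accuracy is unchanged.

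For the diaries, the data are used child by child. Correlation is insensitive to shifts and to changes of scale. The paired t-test looks only at the mean, so large errors in opposite directions cancel. A non-significant t-test with a significant correlation is easily read as agreement when individual diaries are hours apart.

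**Working it through.** The protocol gives no sample size, power or target for these comparisons, so there is no figure of its own to reproduce. What follows is illustration. Product counts and SDs are assumptions, because the documents give neither.

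**1. Photo ratio.** Let S be the scanned products, C the correct photo identifications and F the other items on the photo list.

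- Plan's ratio = C/S. Positive predictive value (PPV) = C/(C+F).
- Assume S = 20 and C = 18. The ratio is 18/20 = 0.90 whatever F is.
- F = 0: PPV = 18/18 = 1.00.
- F = 5: PPV = 18/23 = 0.78.
- F = 20: PPV = 18/38 = 0.47.
- F = 40 (an extreme): PPV = 18/58 = 0.31.

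With S = 20 and C = 18, at most two of the F items can be scanned products given a wrong name. Those two have already cost the ratio its missing 0.10. All the others have no scanned counterpart and cost it nothing.

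**2. Paired t-test and limits of agreement.** Inputs: two-sided alpha 0.05 (stated in the protocol only for the sample-size example in Section 2.3). Section 3.2 allows at most 64 siblings beside 64 index children, and Section 4.4.4 has both wear the GPS, so there are up to 128 children per visit. Assumed SD of the daily differences: 2 to 4 h.

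- Largest non-significant mean bias = t(0.975, n−1) × SD/√n, with t = 1.998 and √n = 8 for n = 64, and t = 1.979 and √n = 11.31 for n = 128.
- 95% limits of agreement = mean bias ± 1.96 × SD.

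| SD of differences | Bias, n = 64 | Bias, n = 128 | Limits around the bias |
|---|---|---|---|
| 2 h | 1.998×2/8 = 0.50 h | 1.979×2/11.31 = 0.35 h | ±3.9 h |
| 3 h | 0.75 h | 0.52 h | ±5.9 h |
| 4 h | 1.00 h | 0.70 h | ±7.8 h |

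More children shrink the detectable mean bias but leave the limits where they were. The n = 128 column treats siblings as independent.

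**3. Both statistics together.** If each method has SD s and their correlation is r, the SD of differences is s × √(2(1−r)), which equals s at r = 0.5. In 4,000 simulated studies per setting with no mean bias and r = 0.5, the t-test was non-significant and the correlation significant in about 94% (n = 64) and 95% (n = 128). At r = 0.3 and s = 3 h the limits are ±7.0 h, and the same pair of results occurs in 65% and 89%. The smallest significant correlation is 0.246 at n = 64 and 0.174 at n = 128.

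**4. Proportional error.** If the questionnaire doubles each child's deviation from the mean and the two means are equal, with s = 3 h for the less variable method, then r = 1 and the mean difference is 0. The limits are ±1.96×3 = ±5.9 h. Neither named statistic sees this.

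**5. The opposite failure.** Take bias 0.1 h and SD of differences 0.25 h. The limits are 0.1 ± 0.49, that is −0.39 to 0.59 h. The noncentrality at n = 64 is 0.1/(0.25/8) = 3.2, and the paired t-test is significant with probability 0.88 (0.99 at n = 128). A very precise method is flagged as different.

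**The case against.** Several points on the other side stand, and they limit what may be inferred.

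- A reader might infer that wrong names from the photos never affect the score. They do when the product was scanned: it leaves the numerator. Only items without a scanned counterpart escape. Some of those may be real products the scanner missed, so calling all of them false would be unfair to the photo.
- A reader might infer that none of the named statistics bears on agreement. That is too strong. The ratio is sensitivity against the declared standard, and the t-test tests mean bias, so a questionnaire that doubled every child's time would show a shifted mean even though it correlates perfectly.
- A reader might infer that a poor method passes a stated criterion. The protocol has no such gate. Under Objective 2, suitability also rests on completeness, comprehension and range of responses, and database entry depends on an undefined judgement of adequate quality.
- Table 8 is a summary, further analyses are allowed, and the cited GPS study might include an agreement index. That cannot be checked here.
- Objectives 7 and 8 are secondary objectives of a pilot.

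Even so, the protocol itself names these statistics and nowhere names a false-positive measure or an index of individual agreement. The numerical quality criteria under Objective 2 cover completeness, precision, recovery and detection, not agreement between methods.

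**Conclusion.** The concern holds in limited form. The photo ratio is sensitivity only; in the illustration 0.90 is compatible with a PPV anywhere from 1.00 to 0.31. The questionnaire–GPS statistics describe association and mean bias. Under an assumed SD of differences of 2 to 4 h/day they can look favourable with limits of agreement of ±3.9 to ±7.8 h, and the t-test can also flag a method that is accurate to within about half an hour. The sizes depend on the assumed counts and SDs; the structural point does not. The named statistics cannot show that a method is suitable. This is not a claim that either method is poor or that a stated threshold would be wrongly met. The change is worth making because the results inform the choice of methods for later sites and possible entry into a public database.

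**What to change.** **Objective 7.** Report PPV (correct photo identifications divided by all photo identifications) beside the existing ratio, with confidence intervals clustered by home. Check photo-only items against the scan before counting them as false, since the scanner may have missed them.

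**Objectives 2 and 8.** Make the mean difference with 95% limits of agreement the main comparison, for daily time at home and in vehicles (the two quantities the Objective 8 text says the GPS model returns), in place of the t-test and correlation. Allow for siblings and repeat visits.

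If kappa by half-hour block is added, first fix how blocks with several ticked locations are handled, for example by counting agreement when the GPS state is among those ticked. Daily questionnaire totals need an allocation rule for the same blocks.

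**Cost.** No new data and slightly more analysis. The reported accuracy may look less favourable.

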Appendix C (The IRB-approved Protocol)

Objective	Measurements Required	Proposed Analysis Approach
8) Use low burden techniques and survey instruments to collect current information on children’s activities, locations, and dietary habits to support exposure models and databases	Survey responses from questionnaire; GPS; accelerometer data	Descriptive statistics of reported time spent in microenvironments and activities; calculation of GPS-based time spent in microenvironments using MicroTrac model; quantitative comparison of questionnaire location results with GPS location results (paired t-test, correlations); quantification of accelerometer-based energy expenditures using accepted modeling methods; descriptive statistics of predicted energy expenditures by microenvironment and activity; coding of activity and location data in time-series format appropriate for exposure modeling
9) Use settled dust to identify and classify indoor fungal populations and functions overrepresented among fungal biota	Fungal DNA extracted from dust samples	Qualitative analyses: HTS; identification and classification of indoor fungal population(s); identification of genes and functions overrepresented among the fungal biota Quantitative analyses: ERMI; correlations; univariate and multivariate analyses; comparisons between pre- and post-renovation time points; renovated and non-renovated homes; comparison of collected dust types
10) Evaluate the feasibility of using a simplified mass balance approach to estimate chemical exposure and dose rates incorporating children’s toenail clippings, other multimedia measurements, and activity information	House dust, soil, hand wipe, surface wipe, duplicate diet, urine, blood, feces, toenail clipping concentrations	Descriptive statistics; univariate and multivariate analyses to compare chemical concentrations; correlations amongst chemicals and media; linear regression modeling incorporating multimedia measurements and survey information; geometric mean and standard deviation for elements measured in multimedia samples by pre- and post-renovation time points

Appendix C (The IRB-approved Protocol)

Objective	Measurements Required	Proposed Analysis Approach
11) Examine the feasibility of obtaining extant community-level data and prepare draft approaches for using such data for children’s community exposure factor assessment and multiple stressor effects on estimates of health risks	Domains of interest include: demographics, socio-economics, households, education/schools, safety/social disorder, birth outcomes, medical access, land use/built environment, playgrounds/greenspace, food access/utilization, transit/transportation, pollutant sources; indicators within each domain will be developed based on availability of extant data at the study location	Qualitative evaluation of success for identifying, accessing, and organizing extant community-level data; draft approaches for regression model analysis with personal and biomarker analyte concentrations and selected community domain indicators; draft approaches for hierarchical models to estimate individual and combined effects of community domain indicators and measured personal residential analytes on asthma-related morbidity measurements

